All experimental participants will be males over the age of 18 and predominantly African Americans. Because we are dealing with health disparities related to AIDU and the intervention was developed at a DCAA and will take place in Newark, NJ, we anticipate that the vast majority of participants will be African American. However, we are not imposing race as an eligibility criterion.

Our pilot study included a balanced sample of men and women and our preliminary findings showed great improvements among the women. While we had hoped to conduct this experiment with both men and women, the reality of the population in Essex County made this impossible at this time.

Women represent only 6% of the populations being released from incarceration in Essex County, NJ. Therefore, unless we expanded the study to additional sites (which is unrealistic given the budgetary constraints), recruiting enough women would not be feasible. We discussed this challenge at our NCCB meeting and collaboratively made the difficult decision to exclude women from the current study. Once the intervention is optimized using a male sample, we will be in a better position to design a larger, multi-site study where we will be able to adapt and test the intervention with women.

We do not anticipate that we will have enough power to conduct significant racial comparisons as we expect that approximately 80% of our sample will be African American. We will, however, conduct valid analysis and explore potential moderation effects on the AIDU outcome to inform planning of future studies that could adapt *Community Wise* for use with other populations.

Women currently make up the majority of the NCCB. The NCCB is racially diverse with African Americans, Latinos, and Whites represented. The only female participants in the study will be members of the NCCB.

Participants in this study are not expected to be under custody, court order to attend the treatment, or any form of limited civil freedom; thus this is not part of the inclusion or exclusion criteria. **No research will be conducted with any subject who becomes incarcerated after enrollment until a research amendment discussing the specific procedures of access to the facility is filed and approved by the IRB.**

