- *Do not encourage clients to participate in the study, rather mention to them that there is a study going on that they can consider joining if they want to.*
- *Do not answer any of their questions about the study. Simply tell them to call the study number if they have any questions.*

If you have any questions about this request, please contact the project director at the e-mail or phone number below:

[name]

Email: [contact]

[contact]

Approved: *YH*
IRB #: *16574*

Dos and Don'ts of Recruitment

If you do all of these things, you should go into every group with approximately 12 confirmed men in order to get 8 of each.

-Ask for Multiple phone numbers for each participant, not just one. This is more important than family/friend numbers. Some people have different cells that are turned off but will be back on. And house lines too, get as many as possible.

-Ask people when they give a phone number during the phone screening, "is this # you're giving me YOUR number?" If not, def ask for additional numbers!!

- Friend and family numbers are only useful if they are people they live with or see every day so when asking for alternate numbers for family/friends, request this specifically. Anything else is a waste of time.

-on the spreadsheet, keep track of who is friends or related to whom. Some participants are friends or related and this will be very helpful in getting in touch with people.

-If someone sounds very unsure/confused or does not have a phone number or permanent living address, schedule them 5-7 days from the date of their call and do not remind them of their appointment. Some people will surprise you and show up and these people will end up being reliable. For the others it is just a good way of weeding them out without rejecting them.

-For all others, schedule them for the following day or the day after whenever possible. Same day is not good and two days you start losing people. Don't confirm appointments that are within this time frame. People are able to remember without reminders and people who end up needing a lot of reminders end up disappearing and taking up too much time re-scheduling over and over. But if the appointment needs to be more than 2 days away, you should remind people.

-If two people are friends, schedule them back to back so they are more likely to come together and one of them will remember their apt or that they have group.

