-Before the suicidal/psychotic questionnaires let people know there is no right or wrong answer and just because they say yes to certain questions doesn't mean they can't participate. Tell them the questions are just to see how they are doing right now. If you don't do this people won't feel comfortable answering honestly and you'll get a lot of conflicting information.

-Stress that the research and intervention are SEPARATE throughout the screenings and baselines.

-For people who miss an appointment with a no call and then call later wanting to reschedule, tell them we have a 2 appt unexcused miss policy and that they will need to call beforehand next time.

-Give yourself a full hour for each screening appt because some people arrive late or early and getting backed up is not fun.

RECEIVED

MAR 21 2016

INST REVIEW BOARD

Approval Date: November 15, 2021
IRB #16574

- Ask people how they are doing, always offer them a comfortable chair, a place to put their bags, lots of snacks and drinks, etc. Make them feel welcome and comfortable.
- Do not take walk-ins. They will usually disappear. Even if you have time to see them, schedule them for the next day if possible. Generally people who insist on being seen the same day are hoping for fast cash and will not be back to attend the groups.
- every time you see someone, give them a bunch of flyers AND business cards and ask them to please tell everyone they know who might be a good fit for the groups. This is how we recruited most people for the pilot.
- Weed people out by their availability during the phone screening so you aren't wasting your time screening someone in person who is not available for the exact group you need to put them in.
- Know the day/time/location of the group by the time you meet with a participant for the first time. Tell them once you what group they were randomized into, date and location of the first group. Give them a business card with this information during the baseline as they leave.
- Ask people if they seem like they might not come to the first group if they are definitely interested. Tell them there are other people waiting to get in if they aren't and it's totally okay if they don't want to come. I found that most people become more committed once they hear they are doing something other people want to do. And if they really don't want to be in it they will tell you.

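### The approved packet conflicts on whether availability for a particular group filters entry, and on whether randomisation precedes the baseline visit or falls at or after its start

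*Combined protocol and SAP*

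**What the plan says.** **Availability.** The Dos and Don'ts of Recruitment sheet tells recruiters to screen callers out by phone if their availability does not fit, so as to avoid "wasting your time screening someone in person who is not available for the exact group you need to put them in". It adds: "Know the day/time/location of the group by the time you meet with a participant for the first time". The end of section 10 says the reverse. Because of randomisation, a group's time and date cannot be scheduled before a man enrols, and many men are likely to be allocated to a time they cannot make. Availability is first asked in the Baseline Survey, as a day-and-hour grid.

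**Order.** Section 18B has the clinician take consent after the clinical screen, randomise those who agree, and then schedule the baseline. The clinical-screen closing script says a man can go no further until he has attended an orientation session, and Table 1 (Study Measures) places informed consent after that session. Section 10 speaks of consent at baseline, and section 19D of enrolment and signature at baseline. Section 8A-1 randomises those who consent. The tip sheet says of the allocated group's details: "Give them a business card with this information during the baseline as they leave".

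**The concern.** An entry filter tied to one group differs from an ordinary eligibility rule. If a recruiter has a particular group in mind when deciding whether a caller goes forward, entry can depend on the intended group. If that group's slot also reveals its condition, allocation concealment is threatened. Such a filter would also go largely unrecorded, because neither screening form has a reason code for it.

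The order matters for two reasons. If allocation comes first, baseline measures are taken when staff may already know the condition. In addition, the tip sheet's instruction to waitlist men who are too intoxicated for the baseline, or not taking it seriously, would then act on men already randomised. That instruction is related to the outcome, alcohol and drug use.

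**Working it through.** No power, alpha or effect-size arithmetic applies. The check is a count of entry rules and a comparison of the statements on order.

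**1. Is availability an entry rule anywhere else?**
- Section 9, factorial-experiment participants: 6 inclusion + 3 exclusion = 9 criteria; 0 concern availability.
- Recruitment Screening form: 9 listed reasons − 1 catch-all = 8 named; 0 concern availability.
- Clinical Screening Survey: 8 listed reasons − 1 catch-all = 7 named; 0 concern availability.

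A man turned away for availability could be recorded only under the catch-all or as a refusal. The tip sheet stands alone on this rule and conflicts with section 10.

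**2. Is the tip sheet current?** The evidence is mixed.
- For carry-over from the pilot: it was received in March 2016 and cites pilot experience ("This is how we recruited most people for the pilot"). The phone-screen form received in February 2017 has no availability item.
- For use in the trial: it says "you should go into every group with approximately 12 confirmed men", whereas section 9 says "Our pilot study included a balanced sample of men and women". It also mentions randomisation: "Tell them once you what group they were randomized into, date and location of the first group". It carries the stamp "Approval Date: November 15, 2021" and is not marked superseded.

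**3. Would the slot reveal the condition?** Groups belong to conditions: section 10 selects focus groups by condition, and the condition-specific handouts have fields for meeting time and facilitator. Section 10 also allows the licensed facilitator to conduct the clinical screen. But no schedule in the documents links slots to conditions, so this step is plausible and not established.

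**4. What order do the sections imply?**
- Section 18B: clinical screen → consent → randomisation → baseline scheduled.
- Closing script and Table 1: clinical screen → orientation → consent.
- Sections 10 and 19D: consent and enrolment at the baseline visit.
- Section 8A-1: only those consenting are randomised.

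If consent is given at the baseline visit and randomisation requires consent, randomisation cannot precede the start of that visit. Section 18B puts it earlier, so the two cannot both hold. No section says that randomisation follows a completed baseline; consent and allocation early in the same visit would satisfy sections 8A-1, 10 and 19D. Sections 8A-1 and 18B both still refer to eight conditions (sixteen in section 10), so that wording does not show which is current. The rule on which facilitator may collect data, and the scheduling of data collection by group, do not settle the order. The procedures figure is not shown.

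**5. Size.** The documents give no count of callers filtered on availability or of men waitlisted at baseline. No bias can be computed.

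**The case against.** The strongest reply is that the tip sheet is a pilot remnant and section 18B is one loose sentence. The sheet's target of eight of each has no clear meaning in an all-male trial and reads like the mixed pilot. The 2021 stamp also sits on tracking sheets that still carry a gender column and three monthly assessments, so it does not show that each page is in force. The zero counts above could equally mean that availability was never a trial rule. Section 18B omits the orientation step, and section 8A-1 refers to a wave sample being randomised, which suggests allocation by wave and not at the clinical screen.

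Most of this stands. It lowers the likelihood that either instruction governed conduct, but it does not remove the conflict: both texts remain in the packet. If the sheet is obsolete, withdrawing it is the remedy. The order conflict does not depend on the sheet.

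The reply is also right about consequences. A reader might infer outcome-related loss that biases the comparison between conditions. The documents do not support that. The instruction is to waitlist, not to exclude, and the tracking workbook has a waitlist sheet with baseline and follow-up columns. On the tip sheet's own account a man receives his group details only as he leaves baseline, so one deferred before finishing would not yet have them. No route to a difference between conditions is shown.

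**Conclusion.** Both conflicts hold on the text. One instruction filters entry by fit to a particular group, while section 10 enrols men before any slot is fixed. One section randomises before the baseline is scheduled, while others place randomisation at or after the start of that visit.

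Three stronger readings are not supported. The documents do not show that the filter was applied in the trial, or that a slot identified its condition, so broken concealment is only a possibility. They do not state that randomisation follows a completed baseline. They show no between-arm bias, and its size cannot be computed.

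This is a cheap improvement of low-to-moderate severity. It rests on treating the tip sheet as part of the current packet because it is not marked superseded.

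**What to change.** 1. Delete the group-specific availability filter from the tip sheet, or replace it with one availability rule that is applied before allocation and is identical for all conditions.
2. Amend section 18B so that orientation, consent, the full baseline and any deferral under the tip sheet are complete before allocation is generated and revealed.
3. Reconcile sections 8A-1, 10, 18B and 19D, the tip sheet, and the closing script with Table 1 to that order.
4. If recruitment is complete, report the order and any availability filter actually used; the free-text explanations on the two screening forms are one source. Keep every man already randomised in the analysis as randomised.

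Adjusting for 30-day use at the clinical screen is optional. That measure precedes randomisation under either order, but adjustment helps only for men randomised and later deferred or missing, under a missing-at-random assumption. It cannot correct an availability filter, because filtered callers never reach the clinical screen.

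The cost is wording and the order of existing steps. Some men would wait for a later wave, and a common availability rule, if adopted, would narrow the sample.

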Data will be generated and collected through face-to-face computer assisted interviews, computer assisted self-interviews, focus groups, and group session audio recordings. This will include brief telephone screenings, clinical screenings, baseline, five post baseline follow-ups, focus groups and intervention sessions. Interested individuals will call the study's confidential phone number and complete a brief telephone screen with a research assistant who will obtain self-reported identifying and eligibility information such as birth date, complete name, last incarceration date and place, gender, current AIDU, and whether they reside in Essex County, NJ. Before completing the phone screen, participants will be given a brief description of the study and they will be informed that the information they release on the phone will be kept confidential and will be used only to verify eligibility (including verification of their last incarceration place and date based on public records). This information will be kept in a password secured Excel file in a password secured laptop at a

locked office at NJCRI. Those found to be eligible will be invited to complete the clinical screen with a licensed clinician at NJCRI. Prior to completing the clinical screen, participants will learn more about the study and the clinical screen. They will sign an informed consent to participate in the clinical screen which will include Mini Mental State Exam, MINI International Neuropsychiatric Interview 6 psychoticism and suicidality modules, and the Global Appraisal of Individual Needs-Substance Problem Scale (GAIN-SPS). Those found to be eligible will learn about the randomization process and the study procedures. The clinician will go through the informed consent and those who agree will be randomized into one of eight experimental conditions and we will schedule the baseline. Participants may take the informed consent with them and think about whether to participate or not, as long as we are still recruiting. Paper data will be kept at a locked file cabinet at NJCRI. A code number and a codename will be assigned to each participant completing the clinical screen and only this code number and codename will be used in the paper and electronic data collection. A master list will be created linking names with code numbers and this list will be kept in a password protected excel file in the PD's computer in a locked office at NJCRI.

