
Another risk to confidentiality refers to the fact that participants who participate in *Community Wise* groups will learn information about other participants that are shared in the group. Group participants will make a pledge in the first group meeting to maintain confidentiality. While we hope that people will abide by this pledge, it is possible that group members share information about you with other individuals. We disclosed this risk to participants in the informed consent noting this risk for *Community Wise* Groups and research focus groups.

It is possible the NCCB members and group facilitators may know some of the potential clinical trial participants as these individuals live and work in Newark, NJ. Potential clinical trial participants may be clients, family members or friends of any NCCB member. The standard protocol for such situations is to ensure that any NCCB member or group facilitator who has a personal relationship with a potential participant does not interact with that person as part of the study or does not have access to data that identifies their family/friend/ client.

Clinical trial participants will be randomized into the 16 conditions. It is possible that participants may not be randomized into their study condition of choice (e.g., some people prefer peer facilitators while others prefer a licensed clinician). We will clearly explain to participants at the orientation

session that we do not know which condition is the most effective since this research has not been done before. We will describe each condition with a great amount of detail and emphasize the importance to conduct the research properly so that we can find out what is best possible intervention package. We will ensure that prior to consenting to the study, participants will be fully aware that they will not be able to choose what condition they will receive and that they will agree to participate in whatever condition they are randomized to. Those who are set on only participating in a specific condition will be discouraged from entering the study prior to the randomization.

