- If someone is too high to do the baseline or is obviously not taking the questions seriously, waitlist them.
- People call the phone mostly between 8:30am-10:30am. Try to keep this time free during the day to take calls.
- Nobody shows up to 9am appointments so only schedule 10am and after.

Incentive and Study Activities
Condition 1 or 2 – Full Intervention

Session	# of sessions	Length in minutes	Who	Where	How much per session
Phone screen	1	5	Research Assistant	Phone	\$0
Clinical Screen	1	20	Clinician	NJCRI	\$10
Baseline	1	90	Research Assistant	NJCRI	\$20
Community Wise Sessions	15	120	Group facilitators	NJCRI	\$2.50 each attended session (paid at month follow-up)
Follow-up during intervention	5	60	Research Assistant	NJCRI	\$20
Focus group	1	90	Research Assistant	NJCRI	\$20
Total earned over 5 months	---	---	---	---	\$187.50

Group #:

Group Meeting Dates:

Group Meeting Time:

Name of Group Facilitator:

Meeting place address:

Office Phone Number:

Incentive and Study Activities
Condition 3 or 4 – Critical Dialogue (CD) and Quality of Life Wheel (QLW)

Session	# of sessions	Length in minutes	Who	Where	How much per session
Phone screen	1	5	Research Assistant	Phone	\$0
Clinical Screen	1	20	Clinician	NJCRI	\$10
Baseline	1	90	Research Assistant	NJCRI	\$20
Community Wise CD and Core Sessions	9	120	Group facilitators	NJCRI	\$2.50 each attended session (paid at month follow-up)
Community Wise QLW Sessions	6	60	Group facilitators	NJCRI	\$2.50 each attended session (paid at month follow-up)
Follow-ups	5	60	Research Assistant	NJCRI	\$20
Focus group (possible)	1	90	Research Assistant	NJCRI	\$20
Total earned over 5 months	---	---	---	---	\$187.50

Group #:

Group Meeting Dates:

Group Meeting Time:

Name of Group Facilitator:

Meeting place address:

Office Phone Number:

Incentive and Study Activities
Condition 5 or 6 – Critical Dialogue (CD) and Capacity Building Project (CBP)

Session	# of sessions	Length in minutes	Who	Where	How much per session
Phone screen	1	5	Research Assistant	Phone	\$0
Clinical Screen	1	20	Clinician	NJCRI	\$10
Baseline	1	90	Research Assistant	NJCRI	\$20
Community Wise CD and Core Sessions	9	120	Group facilitators	NJCRI	\$2.50 each attended session (paid at month follow-up)
Community Wise CBP Sessions	6	60	Group facilitators	NJCRI	\$2.50 each attended session (paid at month follow-up)
Follow-ups	5	60	Research Assistant	NJCRI	\$20
Focus group (possible)	1	90	Research Assistant	NJCRI	\$20

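### A commitment prompt that offers an exit directly follows the step telling men their randomised group, so the recruitment sheet permits selective loss after allocation is known

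*Combined protocol and SAP*

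**What the plan says.** **Recruitment sheet (*Dos and Don'ts of Recruitment*).** Staff are to disclose the allocation at the baseline visit: "Tell them once you what group they were randomized into, date and location of the first group". They then hand it over in writing: "Give them a business card with this information during the baseline as they leave". The next item reads "Ask people if they seem like they might not come to the first group if they are definitely interested", followed by "Tell them there are other people waiting to get in if they aren't and it's totally okay if they don't want to come". The author adds that most men become more committed on hearing that others want the place, and that a man who does not want to take part will say so. The item after that is "If someone is too high to do the baseline or is obviously not taking the questions seriously, waitlist them". The sheet opens with a planning target: "you should go into every group with approximately 12 confirmed men in order to get 8 of each".

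**Order of randomisation and baseline.** Section 18B says of men found eligible at the clinical screen that "those who agree will be randomized into one of eight experimental conditions and we will schedule the baseline". Section 10 and section 19D instead place study consent at the baseline. The closing script of the clinical screen sends eligible men to an orientation session first, then to the baseline questionnaire, then to groups about two weeks later.

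**Discouragement before allocation.** Section 20A: "Those who are set on only participating in a specific condition will be discouraged from entering the study prior to the randomization".

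**Non-attenders.** Section 9 draws focus-group members from an intent-to-treat sample and lists attendance at one session as a separate criterion. Section 10 expects many men to be randomised to groups held at times they cannot attend, and still treats them as enrolled.

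**The concern.** Randomisation protects the comparison only if what happens to a man afterwards does not depend on his condition together with his prognosis. Here a staff member who knows the allocation decides which men hear the prompt. The man also knows his allocation, and he is told that leaving is acceptable and that others want the place.

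The conditions invite unequal responses. On the incentive sheets they run from 3 sessions (core) to 15 (full intervention). Section 20A acknowledges that some men prefer peer facilitators and others clinicians. If leavers were lost or their places refilled, the men remaining in longer or less-liked conditions could be more motivated than those elsewhere, and component and facilitator effects would be mixed with selection.

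The waitlist rule raises a related issue. It acts on intoxication, which is close to the substance-use outcome. Whether it can touch randomised men depends on which order of events applies.

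**Working it through.** **1. Does the prompt reach men who know their group?** The sheet has the allocation disclosed by the end of the baseline, and the prompt is the next item, aimed at attendance at the first group. Read in sequence, the man knows his group. The prompt carries no time of its own, so this rests on its position and its target. It does not depend on whether randomisation falls before or during the baseline, because the sheet has the allocation known when the man leaves that visit.

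**2. Can the waitlist rule act on randomised men?**
- Section 18B order: clinical screen, consent, randomisation, baseline. A man who cannot complete the baseline is already randomised, and waitlisting sets him aside after allocation.
- Order implied by sections 10 and 19D and the clinical-screen script: clinical screen, orientation, consent at or just before the baseline. A man waitlisted before he consents is not yet randomised, so the rule affects who is sampled and not the comparison between conditions.
- Section 18B still refers to eight conditions where section 10 and section 20A have sixteen, so it may be older text. The documents do not settle the order.

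**3. What happens to a man who leaves or is waitlisted?** The tracking workbook has a sheet for waitlisted men. I found no statement that a leaver is replaced, loses his allocation or is dropped from analysis, and none that rules this out. The intent-to-treat sample is named in section 9 but not defined there.

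**4. Figures in the documents.** The documents available give no figure for this loss, so there is none to reproduce. Context:
- 592 / 16 = 37 men per condition, and 592 / 2 = 296 per level of each two-level factor.
- (12 − 8) / 12 = 33% expected shortfall per group. This is the total shortfall from all causes, stated for every group. It does not measure response to the prompt and gives no split between conditions.
- 592 / 48 groups (section 18B) = 12.3 per group, close to the sheet's 12 confirmed men. That fits over-filling in advance at least as well as later refilling.

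**5. Illustration on assumed values.** Suppose removed men are dropped, or replaced by men like those who stayed. Let Δq be the difference between the two levels of a factor in the share removed, and D the outcome gap in SD between removed and retained men, the same at both levels. Then:

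bias = Δq × D; SE = √(2/296) = 0.082 SD; type I error = Φ(−1.96 + bias/SE) + Φ(−1.96 − bias/SE)

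| Δq | D (SD) | Bias (SD) | Type I error |
|---|---|---|---|
| 0 | any | 0 | 5% |
| 5 points | 0.25 | 0.0125 | 5.3% |
| 10 points | 0.5 | 0.05 | 9.3% |
| 20 points | 0.5 | 0.10 | 22.9% |
| 20 points | 1.0 | 0.20 | 68.2% |

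For the third row: 0.10 × 0.5 = 0.05; 0.05 / 0.082 = 0.61; Φ(−1.35) + Φ(−2.57) = 0.088 + 0.005 = 0.093. The calculation treats men as independent and keeps 296 per level. Δq and D are my assumptions, not figures from the documents.

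**The case against.** The strongest reply is that the prompt is a retention device and that missing a group is not leaving the trial. Much of this stands. The sheet presents the line mainly as a way to raise commitment, and it tells staff to stress that research and intervention are separate. Section 9 implies that the intent-to-treat sample includes men who attended no session. Section 10 keeps men who cannot attend as enrolled, and pays $20 per follow-up with session attendance only an add-on. If every man who takes the exit is still followed and analysed as randomised, the bias illustrated above does not arise from the prompt.

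Two further points stand. The sheet's items are not strictly chronological. And a man too intoxicated for the baseline has normally not yet been told his group, so his state is unlikely to be a reaction to it.

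Three stronger readings are tempting but unsupported:
- A reader might infer that randomised men are replaced selectively. The mention of others waiting suggests it, but no replacement rule is written.
- A reader might see a contradiction with section 20A. There is none: that passage concerns men set on a particular condition, while the sheet concerns men unlikely to attend.
- A reader might take the 12-to-8 target as the size of the loss, or split it by condition. It supports neither.

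The objection does not remove the instruction itself. The sheet has staff who know the allocation choose which men to offer an exit. It carries a 2021 approval stamp, so it cannot be set aside as superseded. Men's right to stop at any time does not require staff to raise the exit after allocation.

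**Conclusion.** The point holds in a limited form. As written, the sheet permits selective loss, and possibly refilling of places, after allocation is known, in conditions that differ in length and facilitator. This rests on reading the prompt in its place after disclosure of the group.

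The waitlist rule threatens the comparison only if section 18B's order applies. The passages on consent, baseline and randomisation disagree and must be reconciled.

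The size is unknown. Harm requires both that leavers be dropped or replaced and that removal differ between conditions in a way related to outcome. The documents establish neither. Over the assumed range (5 to 20 points, 0.25 to 1.0 SD) the bias is 0.01 to 0.20 SD and type I error 5.3% to 68%; with no difference in removal it stays at 5%. The case for acting is that the exposure is written into a staff instruction and is cheap to remove.

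**What to change.** - Use the commitment prompt only at the orientation session, before randomisation, and delete it from any contact after allocation.
- State one order of consent, baseline and randomisation, and align sections 10, 18B and 19D, the clinical-screen script and the recruitment sheet to it.
- If a man already randomised cannot complete the baseline, reschedule it and keep his allocation.
- Do not refill a randomised man's place except by fresh randomisation of a new man.
- Define the intent-to-treat set as all randomised men. Keep each on the follow-up list and in the analysis unless he withdraws from the research itself, and report waitlisted and withdrawn men by condition where a condition had been assigned.

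The cost is an edit to the sheet and the affected sections, plus brief retraining. The downside is that some groups may start slightly smaller.
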